## **5.3. Subject Inclusion Criteria**

Subjects must meet the following inclusion criteria to be included in the study:

1. Male or female subjects  $\geq 18$  years old (at the time of surgery) who have undergone Navio System-assisted UKR prior to the date of IRB/EC approval of the study site. This includes UKR procedures with all Unicondylar Knee cemented implant designs.
2. Subject had a primary diagnosis of unicompartmental, non-inflammatory degenerative joint disease, including osteoarthritis, traumatic arthritis, or avascular necrosis, required correction of functional deformity, or required treatment of fractures that were unmanageable using other techniques.

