## 2. STUDY OBJECTIVES

This clinical study will evaluate the 2-year safety and effectiveness of the Navio System in UKR in subjects  $\geq$  18years of age, as demonstrated by revision rate, changes in clinical, functional, and quality of life outcomes over time, radiographic assessments and Adverse Event (AE) incidence and frequency.

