#### **5. STUDY POPULATION**

##### **5.1. Subject Screening and Enrollment**

To eliminate the potential for selection bias, Investigators will consecutively screen subjects by date of surgery, starting with their first Navio-assisted UKR subject. For screening, only information in the medical records will be reviewed. Subjects meeting all eligibility criteria will be listed on a Screening and Enrollment log.

Once a subject has completed the informed consent process, if required by the IRB/EC, the subject will be considered enrolled and assigned a consecutive Subject Identification (ID) number that identifies a single study knee. The subject ID number will be listed on the Screening and Enrollment Log. In the event that a subject has bilateral Navio assisted UKR, only the first treated knee will be enrolled and assigned a Subject ID. The Screening and Enrollment Log is the source in which records all screening and enrollment details are recorded.

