## **5.4. Subject Exclusion Criteria**

Subjects will be excluded from the study if they meet any of the following exclusion criteria:

1. Subject received the Navio System-assisted UKR on the index joint as a revision for a previously failed UKR.
2. Subject, in the opinion of the Investigator, had advanced osteoarthritis or joint disease at the time of surgery and was better suited for TKA.
3. Subject, in the opinion of the Investigator, had a neuromuscular disorder that prohibited control of the index joint.
4. Subject, in the opinion of the Investigator, was morbidly obese.
5. Subject, in the opinion of the Investigator, was contraindicated for UKR.
6. Subject (prospective subjects only), in the opinion of the Investigator, has an emotional or neurological condition including mental illness, mental retardation, drug or alcohol abuse.
7. Subject (prospective subjects only) is a prisoner.

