## **8. SAFETY REPORTING**

Adverse Events (AE) related to the study device (Navio), the unicondylar implant, or procedure including Adverse Device Effects (ADE), Serious Adverse Device Effects (SADE), Unanticipated Serious Adverse Device Effect (USADE), and Device Deficiencies (DevD) occurring from the time of the study procedure until revision or study completion must be recorded on the appropriate CRF and reported. If the event is known to have been previously reported to Smith & Nephew, this must be noted on the CRF. After consent, in addition to all events related to Navio, the unicondylar implant or the procedure, all serious adverse events (SAE), regardless of causality, must be recorded on the appropriate CRF and reported to sponsor and IRB if necessary. Events leading to a revision should be reported at all times regardless of causality.

Adverse Device Effects (ADE) occurring after study completion will be handled as product complaints reportable by the Sponsor and will not be entered into the study database.

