#### **F. Device Deficiency (DevD)**

A DevD is an inadequacy of a medical device with respect to its identity, quality, durability, reliability, safety, or performance. DevD include malfunctions, use errors, and inadequate labeling.

For this study, DevD should be reported when they concern any component of the Navio system as well as its packaging and tools that need to be used during surgery according to the User Manual.

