### **9.3. Evaluability**

All subjects that receive a study device are considered study participants. The following study populations and analysis sets will be defined:

- Safety Population: This will include all subjects that received the study device.
- Full Analysis Set (FAS): This will include all subjects that received the study device.
- Per Protocol Population (PP): This will include all subjects that received the study device, meet the inclusion/exclusion criteria, attend the follow-up assessments, and have no significant protocol deviations. Subjects that are required to be withdrawn from the study under the protocol (e.g. due to revision) will be included regardless of attendance of follow-up visits unless they are deemed to have significant protocol deviations or failed to meet the inclusion/exclusion criteria.

Statistical analysis will be performed using each of the patient populations as follows: analysis of the primary, secondary efficacy objectives will be performed separately using both the FAS and the PP Population. All safety analyses will utilize the Safety Population.

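### Navio cases converted to TKA during surgery fall outside the screening frame, and those finished manually are unclassified, so some device failures can be missing from the safety results

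*Protocol*

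**What the plan says.** The objective in Protocol section 2 concerns the system: "This clinical study will evaluate the 2-year safety and effectiveness of the Navio System in UKR". Protocol section 8 identifies the study device in the same way, asking for "Adverse Events (AE) related to the study device (Navio), the unicondylar implant, or procedure".

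Entry is set by Protocol 5.3, inclusion 1: patients "who have undergone Navio System-assisted UKR prior to the date of IRB/EC approval of the study site". Protocol 5.1 builds the screening list on the same event: "Investigators will consecutively screen subjects by date of surgery, starting with their first Navio-assisted UKR subject". It then says who is logged: "Subjects meeting all eligibility criteria will be listed on a Screening and Enrollment log". Section 5.1 presents consecutive screening as the safeguard against selection bias, and section 10.3 makes a similar claim for the consent waiver.

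Exclusion 2 in Protocol 5.4 removes a subject who, in the investigator's opinion, "had advanced osteoarthritis or joint disease at the time of surgery and was better suited for TKA". Exclusion 5 does the same for anyone judged contraindicated for UKR.

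Protocol 9.3 defines the "Safety Population: This will include all subjects that received the study device", and SAP 7.2 has an equivalent definition. On deficiencies, Protocol 8.1 F says that "DevD should be reported when they concern any component of the Navio system as well as its packaging and tools".

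Neither document defines a Navio-assisted UKR. Neither says how to screen, log or analyse a procedure in which Navio was abandoned or the operation was converted.

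**The concern.** Navio is used only during the operation. Its most consequential failures are those that stop the surgeon from finishing as planned. If entry depends on the operation having ended as a Navio-assisted UKR, entry depends partly on an intra-operative outcome that can reflect how the device performed.

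Consecutive screening does not repair this. It prevents picking and choosing within a list, but not the loss of cases that never reach the list. Because screening begins with each investigator's first case, any conversions in early use would fall in exactly the period sampled.

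At stake are the adverse event, adverse device effect and intra-operative complication results. They could describe a population from which some of the worst device outcomes had already been removed, with no count to show how many.

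**Working it through.** **Step 1. Where each kind of case goes under the text as written.**

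- *Navio used, UKR implanted, malfunction or deficiency on the way.* Eligible. Captured by related-event reporting from the time of the procedure (Protocol 8), the adverse device effect definition, which covers malfunction and use error (8.1 C), deficiency reporting (8.1 F), record-review reporting (8.2) and the SAP's summary of intra-operative complications (SAP 7.5).
- *Navio started, abandoned, UKR finished with conventional instruments.* Not classified. Protocol section 4 foresees partial use, since the surgeon can switch off both cutting-control modes and use the system as an ordinary navigated drill. No rule says how much use makes a UKR Navio-assisted.
- *Navio started, converted to TKA during surgery.* The operation ends without a UKR, so on the natural reading inclusion 1 fails. The case is not on the list screened under 5.1, and no other section asks for a count of attempts.

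**Step 2. Do the safety definitions recover the third group?** Protocol 9.3 counts anyone who received a study device as a participant. Taken alone, that would cover a converted patient who was exposed to Navio. The analysis sets, however, are drawn from enrolled subjects, and this patient is not eligible for enrolment. SAP 5.4 adds to the difficulty: it attaches the term study device to the knee implant and lists Navio separately. On that usage the SAP's Safety Population needs an implant, which again leaves out a conversion to TKA.

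**Step 3. The plan's own figure.** Inputs from Protocol 9.1 and 9.4: control 95.7%, margin 7%, so a limit of 88.7%; n = 115; one-sided 5%; exact binomial.

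- Success needs at least 108 of 115 revision-free: P(X ≥ 108 | 115, 0.887) = 0.0446, and the lower bound at 108/115 is 88.87%.
- Power: P(X ≥ 108 | 115, 0.957) = 87.7%, so the stated minimum of 80% holds.
- Attrition: 115 / 0.9 = 127.8, rounded up to 128.

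The sample size reproduces, and this point does not challenge it.

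**Step 4. How many cases could be missing.** The documents give no rate of abandonment or conversion. Assume a share c of started cases is lost. With 128 enrolled, the missing number is 128 × c / (1 − c):

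- c = 1%: 128 × 0.01 / 0.99 = 1.3
- c = 5%: 128 × 0.05 / 0.95 = 6.7

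**Step 5. What that does to a device-event rate.** Let p be the rate in enrolled cases and f the share of missing cases that are device-related. The rate among all attempts is (1 − c)p + cf, which differs from p by c(f − p). The reported rate is too low whenever f exceeds p. The shortfall is at most c(1 − p), so under 1 percentage point at c = 1% and under 5 points at c = 5%.

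For illustration, with p assumed to be 2%:

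| c | f = 0 | f = 1 |
|---|---|---|
| 1% | 0.99 × 2% = 2.0% | 2.0% + 1% = 3.0% |
| 5% | 0.95 × 2% = 1.9% | 1.9% + 5% = 6.9% |

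The documents supply none of c, f or p.

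**The case against.** The best reply is that this is an undefined term and little more. Inclusion 1 does not ask that the procedure be completed with Navio, and a UKR planned with Navio and finished by hand can fairly be called Navio-assisted. The objective is the system in UKR and the primary endpoint is UKR revision, so a knee without a UKR adds nothing to the main result. Some conversions follow from disease found at surgery rather than from the device, and exclusions 2 and 5 could remove those patients anyway. Section 5.1 also calls the log the source for all screening details, so a careful site might record such cases.

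Much of this stands, and it rules out three stronger readings that a reader might infer.

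- *Every abandoned Navio case is excluded.* Not supported. For a manual finish the text is silent and can be read either way.
- *Device failures drop out of the safety results.* Too broad. In enrolled subjects the reporting routes in step 1 capture them.
- *The true event rate is 3% to 7%.* Those are the f = 1 values in step 5. They need an assumed conversion rate and an assumed 2% event rate, and they treat every lost case as Navio-related.

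The reply does not answer the conversion to TKA. That patient was exposed to the study device, is not on the list that sites are told to screen, and need not be logged. Exclusions judged in retrospect by the investigator make the omission harder to see, because a device-related conversion and a disease-related one can leave by the same route. That a site might log such a case voluntarily is no substitute for a requirement.

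**Conclusion.** The point holds in limited form. Following the plan as written leaves conversions to TKA during surgery uncounted and leaves manual finishes to each site's judgement after the event. Failures that ended the UKR, and possibly those that ended Navio assistance, can therefore be absent from the safety numerator and denominator. This is selection on an intra-operative outcome, at odds with the stated aim of avoiding selection bias, and so goes beyond missing detail.

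The size is unknown. About 1 to 7 missing cases per 128 enrolled follows only from the assumed 1% to 5%, counts every abandoned or converted case as lost, and includes cases that are not device-related. The natural reading of inclusion 1 is itself an interpretation, since the term is undefined.

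A reader might go on to conclude that the study can say nothing about Navio's safety in UKR. The documents do not support that. Two-year revision and safety results in knees that received a UKR and were enrolled remain interpretable for that population. What is limited is any statement about intra-operative safety across all attempts.

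**What to change.** - Define the screening frame in Protocol 5.1 and 5.3 as all attempted Navio-assisted UKRs, with the point at which an attempt starts set by the sponsor.
- Log every attempt with its intra-operative outcome (finished with Navio, finished manually, converted) and the reason, before the other eligibility criteria are applied.
- State that a Navio start finished as a manual UKR is eligible.
- Report abandoned and converted cases, with reasons, beside the adverse event, adverse device effect and device deficiency results, under the same consent or waiver rules as other subjects. SAP 5.4 and 7.13 list no device deficiency summary, so one has to be added. Use one meaning of study device in both documents.
- Keep the primary survivorship analysis on knees that received a UKR, since only an implanted UKR can be revised. Counting conversions as failures would change the question and the power: with success probability 0.957 × (1 − c), power at n = 115 under the protocol's one-sided rule falls from 87.7% to 74.1% at c = 1% and 17.0% at c = 5%.

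The cost is protocol and SAP wording and a few extra operative records per site. Some converted cases may be hard to find in retrospect, and the reported device-event rate may look slightly less favourable. The 115 and 128 do not change.

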## **5.4. Subject Exclusion Criteria**

Subjects will be excluded from the study if they meet any of the following exclusion criteria:

1. Subject received the Navio System-assisted UKR on the index joint as a revision for a previously failed UKR.
2. Subject, in the opinion of the Investigator, had advanced osteoarthritis or joint disease at the time of surgery and was better suited for TKA.
3. Subject, in the opinion of the Investigator, had a neuromuscular disorder that prohibited control of the index joint.
4. Subject, in the opinion of the Investigator, was morbidly obese.
5. Subject, in the opinion of the Investigator, was contraindicated for UKR.
6. Subject (prospective subjects only), in the opinion of the Investigator, has an emotional or neurological condition including mental illness, mental retardation, drug or alcohol abuse.
7. Subject (prospective subjects only) is a prisoner.

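### Exclusions 2 to 5 are investigator opinions formed after surgery with any recorded revision in view, so revised knees can be preferentially screened out and survivorship biased upward

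*Protocol*

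**What the plan says.** **Timing.** Inclusion criterion 1 (Protocol 5.3) admits only patients "who have undergone Navio System-assisted UKR prior to the date of IRB/EC approval of the study site". Every eligibility decision therefore comes after the operation.

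**Evidence.** Protocol 5.1 states: "For screening, only information in the medical records will be reviewed". It sets no cut-off at the date of surgery and no masking to implant status.

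**Criteria.** In Protocol 5.4, exclusions 2 to 5 depend on the investigator's opinion. Exclusion 2 applies if the subject "had advanced osteoarthritis or joint disease at the time of surgery and was better suited for TKA". Exclusion 5 is a general clause: "Subject, in the opinion of the Investigator, was contraindicated for UKR". Exclusions 3 and 4 concern neuromuscular disorder and morbid obesity. None of the four gives a threshold or names a source document.

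**Stated safeguard.** Protocol 5.1: "To eliminate the potential for selection bias, Investigators will consecutively screen subjects by date of surgery".

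**Log.** Protocol 5.1 says: "Subjects meeting all eligibility criteria will be listed on a Screening and Enrollment log". The last sentence of the same section describes the log as the source for all screening and enrollment details. Protocol 5.2 asks for the reason for exclusion on the log, directly after its sentence on subjects who refuse.

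**Reporting.** SAP 7.6 summarises subjects who do and do not complete the study, and accountability by visit. It has no count of patients screened or excluded.

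**The concern.** All screened patients did receive a UKR. To rule afterwards that one of them was better suited for TKA, or was contraindicated, is a hindsight judgement, and a knee already revised invites it more than one that is doing well. The words in exclusion 2 that refer to the time of surgery fix which state is judged. They do not limit the evidence used to judge it.

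The study has a single arm and a historical control, so case selection is its main protection against bias. The primary endpoint is 2-year revision-free survival, tested against 88.7%. If revised knees are excluded at a higher rate than unrevised ones, the estimate rises and a device at the non-inferiority limit passes too often. The analysis sets would not reveal this. The safety population (and the FAS, which is identical) is defined as all who received the device, but a treated patient excluded at screening contributes no data.

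**Working it through.** **Inputs from the documents.** Control 95.7% and margin 7 points (Protocol 9.1, SAP 6.1), so the limit is 95.7 − 7 = 88.7% and the null revision proportion is 11.3%. There are 115 evaluable subjects and 10% attrition. The protocol rule is a one-sided 95% exact binomial bound above 88.7% (Protocol 9.4). The SAP rule is the lower limit of a two-sided 95% Kaplan-Meier interval above 88.7% (SAP 7.10).

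**Reproducing the plan's figure.** With n = 115 and the one-sided exact bound, success needs at most 7 revisions. The exact error at 88.7% is P(X ≤ 7 | 115, 0.113) = 4.5%. Power at 95.7% is P(X ≤ 7 | 115, 0.043) = 87.7%, which meets the stated minimum of 80%. 115 / 0.90 = 127.8, so 128 are enrolled. The sample size is not in question here.

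**How fine the decision is (n = 115).**

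| Revisions | One-sided 95% lower bound | Two-sided 95% exact lower bound |
|---|---|---|
| 6 | 89.96%, pass | 88.99%, pass |
| 7 | 88.87%, pass | 87.86%, fail |
| 8 | 87.80%, fail | 86.75%, fail |

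At the boundary, one knee changes the conclusion.

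**Effect of selective exclusion.** Let e be the share of revised knees, and g the share of unrevised knees, removed by opinion and replaced by the next eligible subjects. Then

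apparent revision = 0.113(1 − e) / [0.113(1 − e) + 0.887(1 − g)].

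Example with e = 0.20 and g = 0: 0.0904 / (0.0904 + 0.887) = 9.2%. False success is P(X ≤ 7) under the one-sided rule and P(X ≤ 6) under the two-sided exact bound. The latter is a no-censoring stand-in for the SAP's Kaplan-Meier interval.

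| e (assumed) | g (assumed) | Apparent revision | One-sided rule | Two-sided stand-in |
|---|---|---|---|---|
| 0 | 0 | 11.3% | 4.5% | 2.0% |
| 10% | 0 | 10.3% | 8.5% | 4.2% |
| 20% | 0 | 9.2% | 15.5% | 8.4% |
| 30% | 0 | 8.2% | 26.7% | 16.0% |
| 20% | 10% | 10.2% | 9.1% | 4.6% |
| 30% | 10% | 9.0% | 17.6% | 9.8% |

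If e = g, the formula returns 11.3% and there is no bias. At the null, 115 × 0.113 ≈ 13 revisions are expected, so e = 10% is about 1.3 knees across up to 10 sites.

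**Do the safeguards close the gap?** Consecutive screening fixes the order of review, not who is then removed by opinion. The consent waiver (Protocol 5.2 and 10.3), which 10.3 also credits with eliminating selection bias, covers subjects who meet the eligibility criteria, so it acts after these exclusions. Even on the fuller reading of the log, it holds a reason for exclusion and not whether the knee was revised.

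**The case against.** Several points on the other side have force.

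- **The log.** A reader might infer from one sentence of Protocol 5.1 that only eligible subjects are logged, so that exclusions leave no trace. The documents do not support that: 5.1 also refers to all screening details, and 5.2 to a reason for exclusion. The sponsor has direct access to source data (11.2) and monitors check compliance (11.6), so an exclusion could be reconstructed. What stands is that the log's scope is inconsistent and that no section requires a check of it against the full list of Navio UKRs.
- **Time anchoring.** Exclusion 2 refers to the time of surgery, and 3 to 5 are in the past tense. The condition must have existed then. What is missing is a limit on the evidence.
- **Outcome known.** A reader might infer that the outcome is always known at screening. It is not: subjects without a 2-year visit may enter the prospective phase, and their final status may be open. Only revisions already in the record are visible.
- **Size.** The calculation puts the truth at the null, and most rows assume that no unrevised knee is excluded. At the planned 4.3% revision rate about 5 revisions are expected (115 × 0.043) against a limit of 7, so one knee decides the result only near the boundary.
- **Consent.** Recording revision status for every screened knee would conflict with Protocol 5.2, which ends data collection for refusers, and with a waiver limited to eligible subjects. The fix must respect this.

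**Conclusion.** The concern holds as a gap in protection against bias, not as a demonstrated bias. Exclusions 2 to 5 are opinions formed after surgery, unmasked, on evidence that need not predate it, and the plan would not report how many patients were removed or why. The protocol's aim of eliminating selection bias is therefore not secured.

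It would go too far to say that survivorship is biased upward. Exclusion unrelated to revision causes no such bias, and neither document gives an exclusion rate. The working shows sensitivity only: false success under the one-sided rule goes from 4.5% to between 8.5% and 26.7% when 10% to 30% of revised knees, and no others, are removed. Those figures assume a true revision proportion of 11.3%, 115 analysed and no censoring. With 10% of unrevised knees also removed, the figures at 20% and 30% fall to 9.1% and 17.6%. The change should be made, because it is specific and its cost is modest.

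**What to change.** 1. **Protocol 5.4:** require exclusions 2 to 5 to be judged only from records dated on or before surgery, and note the supporting document.
2. **Protocol 5.1:** state that every consecutive Navio UKR screened is logged with the criterion and reason for any exclusion. Add implant status only where consent or an IRB/EC waiver permits, and not for refusers. Align the reason-for-exclusion sentence in 5.2 with this.
3. **SAP 7.6:** report the numbers screened and excluded, by criterion.
4. **SAP 7.10:** add a sensitivity analysis of the primary endpoint that adds back subjects excluded only under exclusions 2 to 5, where their data may be used.

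**Cost.** A protocol amendment with IRB/EC approval, extra log entries, and re-review of subjects already screened (SAP 7.15 mentions 27 already analysed). The survivorship estimate may come out slightly lower. Where no waiver covers excluded patients, the add-back analysis will be incomplete, and the report should say so.
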